**PROTOCOL ABSTRACT**

Medical advances in the treatment of HIV/AIDS have improved the life expectancy of HIV-infected individuals. Unfortunately, HIV-infected individuals are three times more likely to use tobacco than those in the general population, but little is known about the mechanisms that underlie these high smoking rates. This will be the first study to test whether the neurocognitive impairments associated with HIV-1 infection may be exacerbated during nicotine withdrawal and increase the probability of smoking relapse among HIV-infected smokers (HIV+), compared to HIV-uninfected smokers

(HIV-). To this end, adult treatment-seeking smokers (N=300; 150 HIV+ and 150 HIV-) will complete this 12-week study, which is divided into two phases: a pre-quit laboratory phase (weeks 0-2) and a treatment phase (weeks 3-12). Subjects will complete two laboratory sessions during the pre-quit phase: once following 24 hours of mandatory smoking abstinence and once while smoking-as-usual (order counterbalanced). A comprehensive cognitive task battery assessing memory, attention, and executive function will be administered during each laboratory session. During the treatment phase, all subjects will receive standard smoking cessation treatment, including counseling (weeks 3-8) and open-label transdermal nicotine (TN) patches (weeks 4-12). The primary outcomes are: 1) cognitive performance following 24-hours smoking abstinence (vs. smoking-as-usual) during the pre-quit phase; and 2) 7-day point-prevalence, biochemically-confirmed abstinence rates at the end-of-treatment (EOT) for the treatment phase.

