#### 2. Design

**Main Study.** This study will use a prospective observational matched-design to test whether HIV+ smokers (vs. HIV-smokers) are more likely to experience cognitive deficits during nicotine withdrawal and whether these deficits are predictive of smoking relapse. As shown in Figure 1, adult treatment-seeking smokers (N=300; 150 HIV+ and 150 HIV-) will complete this 12-week study, which is divided into two phases: a pre-quit laboratory phase (weeks 0-2) and a treatment phase (weeks 3-12). Subjects will complete two laboratory sessions during the pre-quit phase: once following 24 hours of mandatory smoking abstinence and once while smoking-as-usual (order counter-balanced; abstinence biochemically confirmed). A cognitive task battery assessing working memory, sustained attention, and response inhibition will be administered during each session. During the treatment phase, subjects will receive standard smoking cessation treatment, including six sessions of brief individual counseling (weeks 3-8) and eight weeks of open-label transdermal nicotine (TN) patch treatment (weeks 4-12) [34]. The primary outcomes will be: 1) cognitive performance (e.g., verbal and working memory) following 24-hours smoking abstinence (vs. smoking-as-usual) during the pre-quit phase, and 2) 7-day point-prevalence, biochemically confirmed abstinence rates at end-of-treatment (EOT) for the treatment phase. Since randomization is not possible in this study, we will rely on inclusion criteria and matching to reduce the potential for confounding. More specifically, participants will be

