1. **Cardio monitoring sub-study only:** participants may have the non-invasive rhythm monitoring device applied by trained research staff. Participants will be instructed to wear the device for two weeks after which time they will return the device using the study provided pre-paid envelope.
2. Participants will be provided with an iCO monitor (carbon monoxide reader) and will be instructed on how to use it. They will be asked to use this device to measure and report their carbon monoxide levels for the counseling and follow-up sessions.
  - a. The device connects to a smartphone or tablet and uses an app that they would download to display readings. If they are unable to use this device and report abstinence following the Pre-Quit session, they

may be asked to come to our center to complete the carbon monoxide assessment. We will use the recommended biochemically verified 7-day point prevalence abstinence variable which is defined as: (a) no self-reported smoking (not even a puff of a cigarette) for at least the 7 days prior to the assessment, and (b) biochemical verification of abstinence via breath CO (Hughes et al., 2003).

- b. This device is intended for single use as it cannot be sanitized. We will ask that participants not share the device with friends or family to reduce the risk of contamination.
3. Participants may receive a binder containing all information necessary for their counseling sessions. If preferred, this paperwork may also be mailed or emailed to the participant.

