### **Outcomes Variables.**

#### **Abstinence (primary).**

Smoking status will be assessed using the reliable and valid timeline follow-back method (Brown et al., 1998) and by using CO breath samples to biochemically verify the self-report as in prior work (Lerman et al., 2004; Lerman et al., 2015; Schnoll et al., 2015; Schnoll et al., 2010). Participants will be considered to be abstinent if they self-report abstinence (not even a puff of a cigarette) for  $\geq 7$  days prior to each assessment beginning 1-week post-TQD (week 4) and provide or report a CO measurement of less than 5 ppm (Cropsey et al., 2014; Perkins et al., 2013). As per convention, participants are assumed to be smoking if they self-report smoking, cannot be reached to provide data at the time-point, fail to provide a breath sample at the time-point, or provide a breath sample at the time-point  $\geq 5$  ppm (Cropsey et al., 2014; Perkins et al., 2013). The primary outcome will be 7-day point-prevalence abstinence at EOT.

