#### **Other Smoking Measures (secondary).**

The total number of days abstinent during the first 7 days following the TQD, confirmed with CO, will be a secondary outcome measure. We have shown that this measure is highly predictive of long-term abstinence ([name] et al., 2013b). Other secondary smoking outcomes include: prolonged abstinence to EOT (week 12) where relapse is 7 consecutive days of self-reported smoking, after a 2-week grace period; continuous abstinence at EOT (no smoking between the TQD and the follow-up; time to 7-day relapse (no grace period); and lapse (smoking episodes not lasting 7 days) and recovery (return to 24-hour abstinence) events (see (Schnoll et al., 2010)).

**Cessation/Smoking Rate:** Daily smoking (presence and rate) will be assessed at each visit after the Intake Session with the well validated timeline follow-back method (TLFB). These data can be used to assess the timing and rates of lapses (smoking episodes not lasting 7 days), recovery events (return to abstinence), and relapse events, as well as to monitor changes in smoking rates (i.e., # cigarettes/day). These data will also be used to compute and assess secondary measures of smoking cessation (e.g., continuous and prolonged abstinence).

**Carbon Monoxide (CO) Test:** Carbon monoxide will be measured by staff at Intake and the Lab sessions. Following Lab session 2, subjects will be asked to self-report their CO levels using an iCO device (carbon monoxide reader) that will be provided to them at Lab session 2. The iCO smokerlyzer (CoVita, Santa Barbara, CA) is a personal breath smokerlyzer monitor for use with a smartphone or tablet. It works in conjunction with the Smokerlyzer app on iOS and android phones or tablets. The iCO device provides biofeedback from a simple breath test, and it also allows users to track their progress. The app also provides an exhalation guide to coach users on the proper technique to ensure accurate results. The device can be connected to the users' phone through the headphone jack or via Bluetooth. Participants with iOS devices who require adapters will be provided with them by staff. Participants who do not have a smartphone or tablet, or are unable to use the device, will be asked to report to our center for a carbon monoxide assessment if they report abstinence. Since the iCO device cannot be sanitized and does not come with changeable mouthpieces, participants will be advised to limit use of the device to only themselves.

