Risk Assessment Battery d		X										
BASIS-24 d		X										
SF-12 d		X										
Quick Inventory of Depression Symptomatology d		X										

Rhythm Monitoring Device Application c					X					X		
RECRUITMENT PILOT OUTCOMES												
% Eligible at Intake			X									
Attitudes Toward Research		X					X					X
Compared Riskiness Scale d	X	X										
Perceived Coercion Scale d			X									
Previous Experience with Research Studies		X										
Prior Persuasion Questions d			X									
Personal Financial Well-Being		X										

*Note. L1 and L2 = laboratory session 1 and 2, respectively; PQ = Pre-Quit visit; TQD = Target Quit Date; EOT = End-of-Treatment; MINI = Mini International Neuropsychiatric Interview; C-SSRS = Columbia Suicide Severity Rating Scale; HVLT = Hopkins Verbal Learning Test*

a HIV-infected group only

b HIV negative group only

c A viral load assessment, conducted as part of routine clinical care any time between Week 4 and Week 12, will be ascertained through medical record review or contact with health clinic and recorded.

d Only administered if a diagnosis of bipolar disorder is self-reported or revealed via MINI at intake

e Rhythm monitoring devices are worn for two weeks. The second device may be mailed to participants for self-application if an in-person visit is not necessary.

f Measures will primarily be completed remotely via phone or videoconference to limit the length of in-person visits (if applicable)

g Weeks 3-12, participants will self-report using the ICO device. If unable to use the device, and abstinence is reported, participants may be asked to come to our center for CO verification.

h Only administered to participants who were enrolled and active on 3/16/2020 and completed their EOT (Week 12) on or after 3/30/2020.

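### The biochemically confirmed week-12 abstinence outcome can rest on a carbon monoxide value that the participant relays and no one else is required to see, and the plan does not record or analyse its source

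*Combined protocol and SAP*

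**What the plan says.** The Design section names as a primary outcome "7-day point-prevalence, biochemically confirmed abstinence rates at end-of-treatment (EOT"; the Protocol Abstract says the same.

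The definition under Abstinence (primary) needs two things: self-reported abstinence for at least 7 days, and that the participant "provide or report a CO measurement of less than 5 ppm". The same paragraph counts as smokers those who report smoking, cannot be reached, "fail to provide a breath sample at the time-point, or provide a breath sample at the time-point" at or above 5 ppm.

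On who takes the reading, the Carbon Monoxide (CO) Test paragraph says "Carbon monoxide will be measured by staff at Intake and the Lab sessions". After Lab 2, "subjects will be asked to self-report their CO levels using an iCO device". Laboratory Session 2 (Week 2) agrees: "They will be asked to use this device to measure and report their carbon monoxide levels for the counseling and follow-up sessions". The CO note to Table 1 reads "Weeks 3-12, participants will self-report using the ICO device", which includes week 12, the primary time point. The section on the week-12 visit says only that the visit may serve for verification.

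Participants who cannot use the device and report abstinence are directed to the centre for a CO test. The CO Test paragraph states this as a definite request. Laboratory Session 2 and the Table 1 note make it optional.

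**The concern.** The purpose of biochemical confirmation is to have a check on abstinence that does not depend on the participant's word. Here the check can reach the dataset through the participant. No section asks for a screenshot, a data transfer from the app, an observed breath or an identity check. The only advice on sharing the device is given because it cannot be sanitised.

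Two standards of verification therefore apply: staff-measured and participant-relayed. Which one a person gets depends on device access and probably on the COVID period. The groups are not randomised and are matched only on age, race, education and smoking rate, so nothing in the design balances CO source across HIV status.

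If false abstinence is equally common among smokers in the two groups, it shrinks the HIV contrast. If it differs, it can bias the contrast in either direction. Aim 3 is affected too, because its mediation analysis is conditional on a significant Aim 2 effect.

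The existing safeguards do not reach this. Coding missing data as smoking does not catch a false report, which is not missing. The planned Sensitivity Analysis compares pre-COVID with post-COVID completers, and a post-COVID participant may still have had CO measured at the centre.

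**Working it through.** **Text.** The rule for abstinence accepts a reported value, whereas the rule for smoking speaks of a breath sample provided or not provided. A relayed value below 5 ppm satisfies the first rule, and the second does not say whether it counts as a sample. Read with the CO Test paragraph and the Table 1 note, a participant can be counted abstinent at week 12 with no reading seen by staff.

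**Inputs from the plan** (Power Analysis and Sample Size): 150 per group; z-test on log-odds; 5% type 1 error, taken as two-sided because the plan does not say; stated power 80% for 60% v 45%, 50% v 35% and 40% v 25%.

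**Formulas.** With d the log odds ratio,

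- SE = √[1/(150·p₁(1−p₁)) + 1/(150·p₂(1−p₂))]
- power = Φ(d/SE − 1.96)

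**The plan's own figure.** For 40% v 25%, d = ln 2 = 0.693, SE = √(1/36 + 1/28.125) = 0.252 and power is 78.6%, close to the stated 80%. The other two pairs give 74.4% (50% v 35%) and 73.6% (60% v 45%). That shortfall is a separate matter; the 40% v 25% pair is used below.

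**Assumptions that the documents do not supply.**

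- m is the share of true smokers wrongly counted abstinent among those whose CO is self-relayed: 5% or 10%.
- e is the share of participants whose CO is self-relayed. Two values are tried. The first is e = 1. The second is e = 0.43, which assumes even accrual over the 63 months ending June 2022 and a device introduced with remote visits at the end of March 2020: April 2020 to June 2022 is 9 + 12 + 6 = 27 months, and 27/63 = 0.43.
- Observed abstinence rate = p + (1 − p)·e·m.

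Example with m = 10% in both groups and e = 1: 0.40 + 0.60 × 0.10 = 0.46 and 0.25 + 0.75 × 0.10 = 0.325. The difference falls from 15 to 13.5 points. With e = 0.43 the rates are 0.4258 and 0.2823, a difference of 14.4 points.

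| Assumed misreporting (HIV− / HIV+) | e = 1 | e = 0.43 |
|---|---|---|
| Power, none | 78.6% | 78.6% |
| Power, 5% / 5% | 72.6% | 76.1% |
| Power, 10% / 10% | 66.5% | 73.4% |
| Power, 5% / 10% | 46.5% | 65.7% |
| Power, 10% / 5% | 86.6% | 82.3% |
| Type I error, true rates both 30%, 5% v 10% | 9.7% | 5.9% |

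The type I figure is the same whichever group misreports more. In the 10% / 5% row the higher power comes from an exaggerated contrast: with e = 1 the observed rates are 46% v 28.75%, a difference of 17.25 points against a true 15.

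**The case against.** Several points on the other side are fair.

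- A reader might infer that the outcome is simply self-report twice. The text does not support that. The participant must blow into a CO monitor whose app guides the exhalation; the gap lies in identity and in the relay of the number.
- A reader might infer that people without a smartphone are held to a mandatory centre test. The wording is a request in one place and optional in two others.
- A reader might apply the misreporting rates to all 300 participants. The Sensitivity Analysis section describes pre-COVID completers as seen entirely in person, so the exposed share may be well under one. The e = 0.43 column reflects this, but the documents do not say when the device came in.
- Visit and task payments in Subject Compensation follow attendance and compliance, and no stated payment rewards abstinence. This weakens the motive to misreport.
- Nothing in the documents shows that misreporting or device access differs by HIV status. The differential rows are illustrations in both directions.
- A video check cannot be assumed at week 12. Remote Study Participation describes remote sessions by phone, and video is only one of the options for counselling, which ends at week 8.

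These points limit the size of the concern and shape the remedy. They leave the core in place: a relayed value counts, nobody has to see it, and no planned analysis separates it from a staff-measured one.

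**Conclusion.** The concern holds as a gap in verification and documentation of the primary outcome. It does not show that the outcome is biased, and the documents cannot support a claim about how large any bias is.

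Under assumed misreporting of 5% to 10% of smokers in both groups, the loss is about 6 to 12 points of power if everyone is exposed and about 3 to 5 points if 43% are. If misreporting differs by HIV status (5% v 10%), power runs from 46.5% to 86.6% depending on direction, and type I error is about 6% to 10% against a nominal 5%. All of these rest on misreporting rates that the plan does not give; the reading of the text does not depend on them.

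Remote CO testing was a reasonable adaptation and need not be reversed. This is a cheap improvement.

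**What to change.** 1. At week 12, ask each participant who reports abstinence and uses the personal device for a dated screenshot of the app reading, or to show it on camera where the contact happens to be by video.
2. Add one data field for CO source: staff-measured, reading seen, or reported only. Reconstruct it for earlier completers where records allow.
3. Tabulate CO source by HIV status.
4. Pre-specify an Aim 2 sensitivity analysis that counts reported-only values as smoking, and state in advance how an unknown source is handled. Leave the primary definition unchanged.
5. Reconcile the definite and optional wordings of the request to attend for CO, and state whether a relayed value counts as a breath sample.

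The cost is one request at an existing contact and one field, with no extra visits or staff. There are limits. Some true abstainers will not send proof, a screenshot does not show who blew, and the source may be unknown for earlier completers. Counting reported-only values as smoking could also distort the contrast if remote participation differs by HIV status. For these reasons it should be a sensitivity analysis, read alongside the table of source by group.

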## **Rhythm Monitoring Sub-Study Measures.**

### Cardiac Supplemental Medical History.

A supplemental medical history will be conducted remotely or in-person as part of the Intake tasks, to review for sub-study eligibility. The supplemental medical history will be completed by a research staff member and any indications will be reviewed by the study PI/study physician to determine eligibility for the cardio monitoring sub-study.

### Risk Assessment Battery (RAB).

This is a self-report questionnaire designed to assess high-risk behaviors associated with HIV transmission. The measure yields two scores: Drug Risk Behavior (e.g. sharing needles, IV drug use) and Sex Risk Behavior (e.g., exchanging sex for drugs, unprotected sexual activity).

### The BASIS-24.

The BASIS-24 is a 24 item self-report inventory designed to measure mental health status from the patient's point of view. The items cover 6 domains including: depression/functioning, interpersonal relationships, psychotic symptoms, alcohol/drug use, and emotional lability.

### The SF-12.

This measure is used to assess health-related psychosocial functioning. This well-validated, self-report tool measures 8 health-related dimensions: physical functioning, bodily pain, role limitations due to physical health problems, role limitations due to personal or emotional problems, general mental health, social functioning, energy/fatigue, and general health perceptions.

### Quick Inventory of Depressive Symptomatology- Self Report (QIDS).

The QIDS is a 16-item self-report measure designed to assess the severity of depressive symptoms using the criterion symptoms designated by the DSM-IV.

### Atrial Fibrillation (AF) Burden.

AF burden based on non-invasive rhythm monitoring device data collected during two different study period (weeks 0-2 and weeks 8-10). Determination of AF will be confirmed by technicians with no knowledge of the present study, and only episodes of definite AF lasting > 30 seconds will be included (Solomon et al., 2016). These findings will be reviewed by [name], who will be blinded to other clinical characteristics. We will calculate the cumulative burden of AF as the percentage of analyzable wear time spent in AF. Total analyzable wear time will be calculated from the point of activation to the point of last recorded analyzable signal. This method will provide us an opportunity to compare uniformly across participants who may have different amount of device wear time.

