### **Accrual - Cardio Monitoring Sub-study**

Eligible participants enrolled in the parent study will have the opportunity to participate in the cardio monitoring sub-study. We estimate that in order to achieve a sample of 50 smokers (25 HIV+ and 25 HIV-) with usable data, we will need to enroll 60 participants into the sub-study. Recruitment for the cardio monitoring sub-study ended as of March 2020.

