**Figure 1. Study Time Points and Assessments**

matched on age, race, education, and smoking rate.

**Rhythm Monitoring Sub-Study.** This sub-study will explore differences in arrhythmia burden between HIV+ and HIV-smokers and will also look at the relationship between arrhythmic burden and cognitive function. Fifty smokers (25 HIV+ and 25 HIV-) will be asked to wear a non-invasive rhythm monitoring device for two 2-week periods during the course of the study: for two weeks prior to smoking cessation treatment (weeks 2-4) and then two weeks near the end of treatment (weeks 8-10).

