### Non-invasive Rhythm Monitoring (Sub-study only)

The device, developed by iRhythm Technologies Inc (San Francisco, CA), is a FDA-approved, compact (123 x 53 x 10.7 mm), lightweight (34 grams), and water-resistant, patch-based, lead wire-free, single-use ECG monitor that adheres to the left upper chest and provides 14 days of continuous beat-to-beat ECG data. The device has higher fidelity recordings and larger storage capabilities that can provide full disclosure ECG recordings beyond traditional 24-48 hour monitors (i.e., Holter). All rhythm monitoring devices will be purchased from iRhythm Technologies. At the end of the 2-week monitoring period, participants will return the device using a pre-labeled, prepaid mailer to the iRhythm Clinical Center (Lincolnshire, IL), which is an Independent Diagnostic Testing Facility where the data are analyzed. A digital signal-processing algorithm, which has been approved by the FDA for clinical use with oversight by Certified Cardiac Technicians, will characterize potential arrhythmias by detection of the heart rate, irregularity, and morphology.

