#### Data Analysis.

Descriptive statistics (mean, median, standard deviation, skewness, frequency, etc) will be provided for each outcome measure from the rhythm monitoring device and for the sample characteristics (age, sex). Log-transformation will be considered for continuous outcomes with skewed distributions. Multiple comparisons will be corrected and 5% type I error will be maintained to guard against the problem of false positives due to multiple testing.

Aim 1 will use linear regression with AF burden as the primary outcome and HIV status as a between-subjects factor. Cross-sectional associations between arrhythmia burden and cognitive function (Aim 2) and depression indices (Aim 3) at baseline will be assessed using multivariable linear regression with HIV status as a between-subjects factor. All models will include relevant covariates (e.g., smoking rate, age, sex). For our exploratory aim, longitudinal associations between arrhythmia burden and cognitive and psychiatric measures will be assessed using multivariable linear regression relating a) arrhythmia at baseline and b) changes in arrhythmia burden to changes in cognitive function/psychiatric measures. We will test the HIV status by time interaction and include a dichotomous variable for smoking status at end-of-treatment (abstinent vs. relapsed).

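### AF burden in the rhythm sub-study: the written denominator is a span between two end points and does not remove unreadable time inside it

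*Combined protocol and SAP*

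**What the plan says.** The measure is defined in the combined protocol and SAP under Rhythm Monitoring Sub-Study Measures, Atrial Fibrillation (AF) Burden:

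- **Outcome:** "We will calculate the cumulative burden of AF as the percentage of analyzable wear time spent in AF".
- **Denominator:** "Total analyzable wear time will be calculated from the point of activation to the point of last recorded analyzable signal".
- **Numerator:** "only episodes of definite AF lasting > 30 seconds will be included", with technician confirmation.
- **Purpose:** to "compare uniformly across participants who may have different amount of device wear time".

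The device section says that the monitor "provides 14 days of continuous beat-to-beat ECG data". The sub-study Data Analysis section states: "Aim 1 will use linear regression with AF burden as the primary outcome and HIV status as a between-subjects factor". Aims 2 and 3 relate arrhythmia burden to cognition and depression, and an exploratory analysis uses the change in burden between the two recordings.

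Neither the definition nor the sub-study analysis section subtracts unreadable intervals, sets a minimum readable time or adjusts for signal quality. The sub-study accrual section plans to enrol 60 participants to "achieve a sample of 50 smokers (25 HIV+ and 25 HIV-) with usable data", but does not say what makes data usable.

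On timing, the AF Burden section places the recordings in weeks 0-2 and 8-10. The Design section has the first device worn "for two weeks prior to smoking cessation treatment (weeks 2-4". The Laboratory Session 2 (Week 2) section says that the device may be applied at that visit and worn for two weeks.

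**The concern.** The outcome is named as a share of analyzable time, but the sentence that calculates this time gives only a start and an end. An analyst who follows it literally divides by elapsed time. Noise or temporary loss of contact between the two end points then adds to the denominator and can add nothing to the numerator. Two participants with the same AF share in their readable signal would get different scores if their gaps differed, which is not the uniform comparison the section sets out to achieve.

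AF burden is the Aim 1 outcome of the sub-study and is analysed against cognition and depression in Aims 2 and 3. The results are also meant to supply effect sizes for a larger study, so the definition may be carried forward. The documents give one reason why signal quality could differ between recordings. Study staff apply the first device in person, while the second may be mailed to the participant to put on with remote guidance.

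**Working it through.** The plan gives no AF burden, gap fraction or wear-time figure, so there is nothing of its own to reproduce. The check is algebraic, with examples on assumed values.

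**Notation for one recording**

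- S = span from activation to last analyzable signal. The nominal maximum is 14 days × 24 h = 336 h (14 days from the device section).
- R = total readable time within S, and f = R/S, the readable share. The documents do not give f.
- A = confirmed AF time, which can arise only within R.
- b = A/R, the AF share of readable time. The documents do not give b; 5% is assumed below.

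**Formulas**

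- Literal rule: A/S = (A/R) × (R/S) = b × f.
- Readable-time denominator: A/R = b.
- Relative shortfall of the literal rule: 1 − f.

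Since f cannot exceed 1, the literal rule can equal or understate burden over readable time and can never overstate it.

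**Example with S = 336 h and b = 5% (f and b assumed)**

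| f | R (h) | A (h) | Literal rule A/S | Readable-time A/R |
|---|---|---|---|---|
| 0.95 | 319.2 | 15.96 | 4.75% | 5.00% |
| 0.90 | 302.4 | 15.12 | 4.50% | 5.00% |
| 0.80 | 268.8 | 13.44 | 4.00% | 5.00% |
| 0.70 | 235.2 | 11.76 | 3.50% | 5.00% |
| 0.50 | 168.0 | 8.40 | 2.50% | 5.00% |

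**Cases the literal rule handles correctly**

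- *Early removal, no gaps:* with the device off at day 7, S = R = 168 h and A = 8.4 h, so 8.4/168 = 5.0%. Time after the last signal is already outside the span.
- *No AF:* A = 0, so both rules give 0.
- *Same f for everyone:* each mean becomes f × mean and each SD becomes f × SD. Then d = f(difference)/(f × SD) is unchanged, and so are r and the t statistic. Only the absolute burdens, and differences in percentage points, shrink by the factor f.

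**Cases where it distorts**

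- *f differs by group:* with b = 5% in both groups, f = 0.95 in one and 0.80 in the other gives 4.75% and 4.00%. That is a false difference of 0.75 points, or a ratio of 4.00/4.75 = 0.84.
- *f differs between recordings:* the same two values in one person would appear as a fall of 0.75 points with no change in b.
- *f varies between participants:* this adds variation unrelated to b. If f is also related to cognition or depression, it feeds directly into the Aim 2 and 3 associations.

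**The case against.** The strongest reply is that the sentence names the quantity as analyzable wear time twice. On that reading, the two end points mark the window within which analyzable signal is added up, and gaps were always meant to be left out. This may well be the intention. It does not settle the matter, because the written calculation gives only end points and no other section supplies the subtraction. Two analysts could compute different outcomes from the same text.

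Other parts of the reply stand in full:

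- A reader might infer that anyone who wears the device badly will look healthier. The documents do not support that. Stopping early is handled, and the stated purpose is met for differing length of wear. Only gaps before the last signal matter.
- A reader might infer that the HIV comparison is biased, or biased against the hypothesis. Nothing in the documents says that readable share differs by HIV status. The 0.84 ratio comes entirely from the assumed split, and the opposite split would reverse it.
- A reader might infer that the effect sizes passed to a larger study must be wrong. A common readable share leaves d and r as they are.
- The quantity b is AF per readable hour. It equals the burden over the whole span only if AF is as frequent in unreadable time as in readable time, which cannot be checked.
- The device is described as giving continuous data, and ten enrolments are allowed for loss of usable recordings (60 − 50), so gaps may be small in the recordings analysed.
- This is a pilot sub-study of 50 people. The main study's primary outcomes are untouched.

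**Conclusion.** The definition needs correction, but no bias has been shown. Taken literally, the rule returns burden over readable time multiplied by the readable share. The relative shortfall is 1 − f: 5% at a 95% share and 20% at 80%. The direction is certain under the literal reading. The size is not known, because the documents give no readable share and every value of f and b used here is an assumption.

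The HIV contrast, the associations with cognition and depression, and the change between recordings are distorted only if the readable share varies between groups, participants or recordings. Mailing of the second device makes variation between recordings plausible, but does not demonstrate it.

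The conflict over the first monitoring window is real and separate, and it adds no weight to the denominator point. A reader might conclude that no weeks 0-2 recording can exist. The text supports only that the sections disagree, since the Laboratory Session 2 section says that the device may be applied then.

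**What to change.** In the AF Burden section, state that for each of the two recordings the denominator is the summed duration of readable ECG between activation and the last analyzable signal, with unreadable intervals excluded. Reporting the readable share by HIV group and by recording would show whether the choice of denominator mattered.

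Separately, reconcile the weeks 0-2 window in that section with the weeks 2-4 window under Design and with device application at Laboratory Session 2.

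The cost is one sentence of definition, one correction of timing and a recalculation from ECG recordings already collected. No new participant data are needed, and the end of sub-study recruitment in March 2020 is no obstacle.
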